Participants will attend Addenbrooke's Oral-Maxillofacial Laboratory for the measurement of the bespoke MAD approximately 1-2 weeks after their baseline visit with fitting 2 weeks later. Each appointment will take 20 minutes. In order to ensure devices are not used until the designated treatment period the bespoke MAD will be sent directly to the study team at Papworth Hospital.

Randomisation

Eligible participants who have given informed consent and satisfy all inclusion/exclusion criteria will go forward to the randomised trial. All participants will have a 6 week period of treatment in each of the 3 treatment arms and 4 weeks in the no treatment control arm. Randomisation will take place once eligibility has been confirmed following measurement for the bMAD and Meditas have confirmed that the impression sent by the participant is adequate to make the SP2 device. The trial team will contact Papworth R&D Department on [name] to receive the randomisation sequence which will be generated by the trial statistician. Further details on the randomisation strategy is included in Section 7.

The first treatment period will begin within four weeks of randomisation.

Intervention schedule: Following the manufacture of the MADs, participants will start the first treatment arm. All participants will receive each MAD for a period of 6 weeks (or no treatment control for 4 weeks) in a randomised order. The MAD will be posted to the participant a few days before the start of the treatment period (or letter advising of no treatment according to participant's intervention schedule) and will be asked to start using the device immediately. Participants will also be asked to complete the daily sleep diary.

The first 2 weeks of each treatment period will act as an acclimatisation phase to give participants time to adjust to each device and will not be considered part of active treatment. The no treatment control period will last 4 weeks.

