Adherence to treatment will be assessed using patient sleep diary. Participants will be asked to record the number of hours MAD was used each night and number of nights used each week. Adherence defined as use ≥ 4 hrs per night and ≥ 5 nights per week. If the participant has not completed the patient diary they will be asked to make their best estimate of their hours/nights use.

Stage of trial	Data to be collected					
Screening	Confirmation of eligibility and application of					
	inclusion/exclusion criteria					
Baseline	Basic participant characteristics (age, sex, body mass index					
	(BMI), neck circumference, waist-hip ratio, cardiovascular					
	disease risk factors, blood pressure)					
	Respiratory PSG					
	ESS, FOSQ					
	HRQoL measures – SF-36, EQ-5D and SAQLI					
	Health care usage and driving questionnaire (RTAs)					
Crossover Treatment Periods 1-4	Two week acclimatisation phase					
	Adherence/Retention					
	Tolerability					
	Participant contact with research staff/maxillofacial laboratory					

	Four week treatment phase
	BMI, neck circumference, waist-hip ratio, blood pressure
	Respiratory PSG
	ESS, FOSQ
	HRQoL measures – SF-36, EQ-5D and SAQLI
	Daily sleep diary (including Partner VAS snoring score)
	VAS satisfaction with MAD
	Health care usage and driving questionnaire (RTAs)
	Side effects, withdrawals and adherence.
Treatment Period 4	Participant MAD / no treatment order of preference
Follow up Years 1 - 2	ESS, FOSQ
	HRQoL measures – SF-36 and SAQLI
	Tolerability
	Side effects, withdrawals and adherence
	BMI
	Bite measurement

Table 4. Outcome Measures Collection

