4. ECONOMIC EVALUATION

4.1 Economic Evaluation of the Crossover RCT: McDaid et al [9] concluded that MAD/dental devices may be a treatment option for moderate disease but it remains unclear precisely what type of device may be effective. This was a result of a lack of high quality evidence on their effectiveness. The economic evaluation element of the cross-over trial will provide descriptive data on the resource use, unit costs and health state utilities observed during the 4-week period. The parameter data obtained in the cross-over trial will allow the key uncertainty about the MAD devices to be addressed in a reanalysis of the long term cost-effectiveness model of McDaid et al [9].

Efficacy Parameter Estimates: Health state utilities will be elicited from participants in the cross-over trial using the EQ-5D with the UK social tariff [10]. Systolic blood pressure results will also be collected.

Resource Use and Unit Costs: Resource use and unit costs are being primarily collected to be incorporated into the long term cost-utility. However, mean costs by intervention will be reported for the four week cross-over trial. The perspective for collecting the costs of resource use will be that of the NHS and Personal Social Services (PSS), as advocated in the NICE reference case [11]. Trial protocol driven costs which do not affect participant care outcomes such as administering research questionnaires will be omitted and only health service cost will be included.

Resource use: Resource use data will be collected for the duration of the trial. The type of MAD unit (SP1, SP2 or bMAD) will be recorded as will the frequency of clinic contact (face–to-face clinical contact and telephone consultation) and primary care visits relating to OSAH.

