Unit costs: MAD unit costs will be obtained from the finance department of Papworth Hospital. Unit costs for clinician time including labour, capital and overheads will be taken from national estimates [12]. Any medication costs will be taken from the NHS electronics drug tariff [13] or the British National Formulary [14]. The unit costs of any hospital procedures will be taken from the NHS reference costs [15]. In the absence of national estimates, unit costs will be taken from published sources and centre specific costs for Papworth Hospital. Unit costs will be applied to the resource use identified for each participant to obtain mean costs for the entire period of the trial. Costs will be reported in 2007/2008 pounds.

Within-Trial Economic Analysis: Health state utility data will be converted to quality adjusted life years (QALYs) for the four week time horizon of the trial using the area under the curve method. To avoid bias and increase precision in estimates regression adjustment will be applied to costs [16, 17]. Independent variables in the regression adjustment will include MAD group and the potential confounding variable of participants' weight. In addition to regression adjusted results, raw scores will be reported for completeness. Results will be expressed as means accompanied by their 95% confidence intervals. In the event that descriptive statistics suggest skewness of the cost data distribution bootstrap replications will be performed to establish the robustness of results.

- **4.2 Long-term Economic Model:** The aim of the long term economic model is to determine the cost effectiveness of MAD devices for the treatment of OSAH. The objectives are to:
 - 1) Determine the cost effectiveness of MADs compared to a no-treatment control
 - 2) Determine the cost effectiveness of MADs compared to all relevant NHS comparators (no treatment, CPAP, conservative care)

Methods: A cost-utility analysis will be conducted to establish the cost-effectiveness of alternative treatments for OSAH. This will be done by populating a probabilistic Markov cohort process model with the best available data on efficacy, QALYs, resource use and costs.

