All statistical analyses and reporting will comply with the CONSORT guidelines where possible [18, 19]. In particular, we intend to follow up all participants irrespective of their level of compliance with the MAD and include all periods in the analysis using 'intention to treat'.

There are 3 main features to consider in the analysis of crossover trials, treatment comparisons, period effects and carryover. Given the nature of the treatments (external devices designed to control symptoms) and the inclusion of a 1 week washout between MAD periods, carryover effects can be ignored. In theory, period effects are unlikely but with all participants required to assess all 4 treatments and stay in the trial for approximately 7-8 months it would be unwise to ignore their possibility. In addition, if compliance is related to time in the study, a period effect may be induced. Thus, in addition to a design that retains some balance even if there is some participant attrition (see section 3.3.9), we will include period effects in the analysis.

Analyses: Exploratory analysis will look at mean differences between treatments by period pair. Treatment effects will also be plotted over time to further explore period effects. The main inferential analysis will

employ linear mixed models with participants included as a random effect and treatment and period as fixed effects. Treatment x period interactions will also be explored although power to detect these second order effects is likely to be limited. There is discussion among statisticians about the relative merits of random and fixed effects for participants and this will be the subject of sensitivity analysis.

The initial analysis will include all participants who complete at least 2 treatment periods. If there are substantial missing data sensitivity analysis surrounding assumptions of 'missing at random' will be undertaken. Similar analyses will be undertaken on a logistic scale for binary outcomes such as the probability of a complete response to treatment (AHI reduced to fewer than 5/hour).

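### Section 4.1 gives two costing windows for arms of unequal length, and names a cost regression without a participant or period term

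*Protocol*

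**What the plan says.** **Costing window.** Section 4.1, on resource use and unit costs, says that "mean costs by intervention will be reported for the four week cross-over trial". The unit-cost paragraph of the same section applies unit costs to each participant's resource use "to obtain mean costs for the entire period of the trial". Resource use is collected throughout the trial, and QALYs are calculated over four weeks.

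**Period lengths.** Section 3.4 states: "All participants will receive each MAD for a period of 6 weeks (or no treatment control for 4 weeks) in a randomised order". Under Section 3.1, a one-week washout follows active treatments only. The first two weeks with each device are acclimatisation, which Section 3.4 does not count as active treatment. Table 4 nevertheless lists "Participant contact with research staff/maxillofacial laboratory" among the data collected in that phase. The bespoke device is measured and fitted at Visits 3 and 4, before the first treatment period.

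**Cost model.** The purpose is stated as follows: "To avoid bias and increase precision in estimates regression adjustment will be applied to costs". On its terms, the protocol says "Independent variables in the regression adjustment will include MAD group and the potential confounding variable of" participants' weight. On reporting: "Results will be expressed as means accompanied by their 95% confidence intervals". A bootstrap is added if costs look skewed, with no resampling unit given. For the main inferential analysis, by contrast, Section 7 will "employ linear mixed models with participants included as a random effect and treatment and period as fixed effects".

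**The concern.** Two analysts could each follow Section 4.1 and produce different costs, one set on a different horizon from the QALYs. The choice matters because the conditions differ in length and no rule says how acclimatisation, washout or fitting costs are allocated or rescaled. The main comparison exposed is device against no treatment. The effect also carries forward: Section 4.2 takes resource use and unit costs for the device and no-treatment arms from the crossover trial into the lifetime model.

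Separately, each participant supplies up to four cost records, one per condition. A regression on treatment and weight alone treats those records as independent and gives up the within-person pairing that is the reason for a crossover. Precision is one of the two stated aims of the adjustment, and the term most likely to deliver it is not named.

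**Working it through.** **Inputs.** Device period 6 weeks, no treatment 4 weeks, washout 1 week after devices (Sections 3.1 and 3.4). Eight sequences and 72 completers (Section 7). The within-person correlation of costs, ρ, is not in the protocol, so a range is assumed. Here ρ means the correlation left after adjusting for weight.

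**Step 1: the plan's own figure.** Section 4 gives no standard error, interval width or power for costs. The only precision figure is the trial's sample size: ((1.96 + 0.84)/(1/3))² = 70.6, so 71 by the normal approximation, against 72 stated; the exact paired t calculation gives 73. Then 72/0.8 = 90. The figure reproduces and is not in dispute. It rests on the standard deviation of a within-participant difference, so the trial was sized on the assumption that pairing is used.

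**Step 2: costing windows.** Let background contacts cost *c* per week in every condition.

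| Window | Device weeks | No-treatment weeks | Ratio | Difference from length alone |
|---|---|---|---|---|
| Four-week treatment phase | 4 | 4 | 1.0 | 0 |
| Acclimatisation included | 6 | 4 | 1.5 | 2*c* |
| Washout also included | 7 | 4 | 1.75 | 3*c* |

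The first row is fair on time, but it omits 2 of the 6 device weeks with the contacts recorded in them. It also omits the two bespoke-device appointments unless they are inside the device unit cost.

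**Step 3: interval width without a participant term.** With variance σ² per record and *n* participants, the variance of a treatment difference is 2σ²(1 − ρ)/*n* when pairing is used and 2σ²/*n* when records are treated as independent. The ratio of standard errors is 1/√(1 − ρ), and the actual coverage of a nominal 95% interval is 2Φ(1.96/√(1 − ρ)) − 1.

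| ρ (assumed) | Width ratio | Actual coverage |
|---|---|---|
| 0 | 1.00 | 95% |
| 0.3 | 1/√0.7 = 1.20 | 98.1% |
| 0.5 | 1/√0.5 = 1.41 | 99.4% |
| 0.7 | 1/√0.3 = 1.83 | 99.97% |

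A simulation of the eight sequences with 72 completers compared ordinary regression on treatment and weight with the paired analysis (1,000 runs per value; weight unrelated to cost). The standard error ratios were 1.20, 1.41 and 1.83, with coverage 0.977, 0.994 and 1.000.

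**Step 4: period.** Across the eight sequences each treatment appears exactly twice in every period. With complete data, leaving out period therefore costs precision but causes little bias; dropout can disturb that balance.

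**Step 5: weight.** Over a trial of this length weight should be nearly constant within a person (an assumption). A characteristic that is the same under all four conditions does not materially confound a balanced within-person comparison. It can explain only part of the between-person variation that a participant term removes in full.

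**The case against.** The strongest defence is that the list of regression terms is open. It says what the model will include, not all that it will contain, and an analysis plan or health-economics plan that is not shown may add participant and period. Section 7 shows that the team understood the design. This stands: a reader might infer that the crossover structure has been discarded, but the text shows only that it is not specified for costs. Nor does the protocol say that single records will be bootstrapped.

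Other stronger readings also fail:

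- **Misleadingly narrow intervals.** With positive correlation the error runs the other way. Intervals for differences are too wide, and intervals for single-arm means, which are what Section 4.1 expressly promises, do not depend on the between-treatment correlation.
- **A built-in cost gap between devices and no treatment.** The gap arises only under whole-period costing and is zero under the four-week window. The 1.75 ratio also requires washout to be charged to the device, which no section proposes. Some acclimatisation contact is a genuine device cost.
- **A changed cost ranking among devices.** All three devices have the same 6-week period and the same washout, so unequal length cannot reorder them.
- **Lost fitting costs.** Face-to-face and telephone clinic contacts and calls to the laboratory are recorded, and device unit costs are applied. The protocol does not say whether the bespoke unit cost covers measuring and fitting, so the loss is possible but not shown.
- **Weight is useless.** In a model without a participant term, weight may absorb some between-person variance and so gain some precision.

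Section 4.1 also calls the within-trial economic data descriptive, and the primary outcome is untouched. That limits the impact but does not remove it, because the trial's resource use feeds the long-term model.

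**Conclusion.** The contradiction in the costing window stands on the protocol's wording alone and needs no assumption. Its size is a ratio of 1.0, 1.5 or 1.75 in the time available for background contacts, device against no treatment, depending on the reading. The monetary effect cannot be given because the protocol has no weekly cost.

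The regression point is conditional. If costs are modelled on treatment and weight alone, intervals for between-treatment differences are about 1.20 to 1.83 times too wide for assumed correlations of 0.3 to 0.7, with no error at 0. Weight cannot stand in for the participant term. Both matters should be settled before the economic analysis; neither affects the clinical results.

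**What to change.** In Section 4.1:

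1. State one costing window, matched to the QALY horizon.
2. Cost the device, impression and fitting as a separate set-up item, and say whether the bespoke unit cost already includes the measuring and fitting visits.
3. Include acclimatisation contacts attributable to the device.
4. Put recurrent contacts on a common time basis in all four conditions, and say how washout is handled.
5. Model costs with participant as a random effect and treatment and period as fixed effects, as in Section 7, and stop describing weight as a confounder of the treatment comparison.
6. If bootstrapping is used, resample whole participants so that each person's records stay together.

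The cost is a few sentences and a small amount of extra analysis. The data are already collected, and no visit or assessment changes.

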5.1 Source Documentation

Data will be collected by a Clinical Research Assistant (CRA) who is not involved in the routine care of the participants and who will record the data on electronic case report forms (CRFs). All data will be anonymised with participants assigned a participation number at randomisation into the trial.

The investigator/clinical research assistant will maintain source documents (patient's hospital case notes) for each patient in the study, consisting of all demographic and medical information, including respiratory sleep study results. A copy of the consent form and patient information sheet will also be filed in the patient's case notes. All information in the CRFs, apart from the questionnaires, will be traceable to and consistent with the source documents in the patient's hospital case notes (Ref. ICH/GCP 4.9.2).

The questionnaires will be scanned by the Papworth R&D department and entered onto a database which will be password protected. The R&D Unit will undertake periodic audit and monitoring.

5.2 Labeling of Source Documentation

The patients' hospital case notes are to be labelled in the following way to indicate that the patient is randomised into a clinical trial:

• An alert sticker to be stuck on the inside front cover of the patient's notes:

Patient consented to research trial:
TOMADO

Date of consent:

Do not destroy notes before 15 years from this date

• To be stuck on the communication/history sheet page:

Patient randomised into

The TOMADO Trial: Crossover Randomised Controlled $\underline{\mathbf{T}}$ rial (RCT) of $\underline{\mathbf{O}}$ ral $\underline{\mathbf{M}}$ andibular $\underline{\mathbf{A}}$ dvancement $\underline{\mathbf{D}}$ evices (MAD) for $\underline{\mathbf{O}}$ bstructive Sleep Apnoea-Hypopnoea (OSAH). CI: [name]

Research Team [name] Or [name]

When a patient completes or if they are withdrawn from the study a red strike through line will be drawn through the second label.

5.3 Data Collection

Data will be recorded on a Formic database produced by Papworth R&D department. Formic is a PC software that allows pre-designed questionnaires to be scanned for data-capture and subsequent analysis. The five questionnaires completed by the participants (SF-36, SAQLI, EQ-5D, ESS and FOSQ) will be scanned into Formic whereas all other data will be entered manually from the source data. The following instructions should be followed for the participant questionnaires:

Originals/photocopies

- Do **not** photocopy the forms. Further supplies can be supplied from the Formic office in the R&D department ([name]).
- The forms should be completed in black or blue ink.

Initials/Characters

- Patient initials must be written in upper case letters.
- If there are only two initials, complete the first and third boxes and put a dash in the second box.
- The initials for a patient must be in the same format on all the forms throughout the study.

Errors

- If an error is made when answering yes/no boxes, fill the box in completely and place an **X** in the correct box.
- If an incorrect entry is made in a box which needs to be amended e.g. a date box, cross out the incorrect entry and enter the correct response in the box or write the answer as close to the outside of the box as possible.
- If there are multiple errors on the same page it is advisable to complete a new form.
- All corrections made by trial staff should be initialed and dated and explained, if necessary (Ref. ICH/GCP 4.9.3).

Free Text

Free text cannot be scanned but is analysed separately

Incomplete Data

Ensure that all sections of the forms are completed or that an explanatory comment is added

6. Outcome Measure Analysis

Primary outcome measure

A NHS Polysomnographer independent of the research team and thus who is blinded to treatment allocation will analyse respiratory PSG studies in order to calculate AHI.

Secondary outcome measures

Secondary outcomes will be administered by the CRA on pre-prepared CRFs. Participants cannot be blinded as they are likely to be aware or will be able to divulge which device they are using.

7. Statistical Analysis

Randomisation: Eligible participants who have given informed consent and satisfy all inclusion/exclusion criteria will go forward to the randomised trial. All participants will have a 6 week period of treatment in each of the 3 treatment arms and 4 weeks in the no treatment control arm. The order in which the treatments are used will be decided according to a computer-generated random number sequence. A common randomisation strategy for crossover trials of this kind is based on Latin Squares designs in which participants are randomised in blocks of 4, with each treatment being represented in each period. These designs are both efficient and well balanced for period. Williams' Latin Squares are particular types of Latin Squares that are efficient and have attractive properties if some of the participants fail to complete all 4 periods (providing most participants do complete all periods). For this reason the randomisation will be based on 2 related Williams' Latin Squares designs, with participants randomised in blocks of 8 to ensure good treatment by period balance. Sequences for each block of 8 participants will be as follows.

Sequence	Period 1	Period 2	Period 3	Period 4
1	A	C	D	В
2	В	D	C	A
3	C	В	Α	D
4	D	A	В	C
5	A	D	C	В
6	В	C	D	A
7	C	A	В	D
8	D	В	A	C

Although randomisation in blocks of 8 will mean that for every eighth participant the sequence will be predictable this is considered to be less important in a crossover trial.

Sample size calculation

We have based sample size estimation on hypothesis testing rather than precision. In the published reviews considered in Section 3.2, the difference in AHI between MAD and sham MAD was of the order of 10-15 units, with a standard deviation of the difference of approximately 20, and effect size between 1/2 and 3/4. Differences between active MAD are likely to be smaller, with minimum clinically important effect sizes of the order of 1/3. An effect size of 1/3 suggests a sample size of 72 participants for 80% power to detect the effect with 2-sided significance of 5%. Allowing for 20% loss to follow up we plan to recruit a sample of 90 participants, each having all 4 treatments.

ADDENDUM: To ensure the randomisation target of 90 is reached and avoid stop-start recruitment we will screen an extra 6 patients. If all of the extra 6 patients are eligible the maximum number randomised will be 96.

Statistical Analysis

All statistical analyses and reporting will comply with the CONSORT guidelines where possible [18, 19]. In particular, we intend to follow up all participants irrespective of their level of compliance with the MAD and include all periods in the analysis using 'intention to treat'.

There are 3 main features to consider in the analysis of crossover trials, treatment comparisons, period effects and carryover. Given the nature of the treatments (external devices designed to control symptoms) and the inclusion of a 1 week washout between MAD periods, carryover effects can be ignored. In theory, period effects are unlikely but with all participants required to assess all 4 treatments and stay in the trial for approximately 7-8 months it would be unwise to ignore their possibility. In addition, if compliance is related to time in the study, a period effect may be induced. Thus, in addition to a design that retains some balance even if there is some participant attrition (see section 3.3.9), we will include period effects in the analysis.

Analyses: Exploratory analysis will look at mean differences between treatments by period pair. Treatment effects will also be plotted over time to further explore period effects. The main inferential analysis will

employ linear mixed models with participants included as a random effect and treatment and period as fixed effects. Treatment x period interactions will also be explored although power to detect these second order effects is likely to be limited. There is discussion among statisticians about the relative merits of random and fixed effects for participants and this will be the subject of sensitivity analysis.

The initial analysis will include all participants who complete at least 2 treatment periods. If there are substantial missing data sensitivity analysis surrounding assumptions of 'missing at random' will be undertaken. Similar analyses will be undertaken on a logistic scale for binary outcomes such as the probability of a complete response to treatment (AHI reduced to fewer than 5/hour).

Regression analyses will be conducted to assess the effects of baseline AHI, ESS, age, sex, BMI, neck circumference and waist-hip ratio on subsequent AHI and ESS scores. These analyses will also explore interactions between these variables and treatment effects although we accept that there will be limited power, so results will be considered as hypothesis generating. In addition, one subgroup analysis is planned, concentrating on participants who decline CPAP vs. those with mild-moderate OSAH for whom CPAP is not indicated.

8. Strengths and Limitations

This pragmatic trial was designed to allow the comparison of the clinical and cost effectiveness of three types of MAD in the treatment of mild to moderate OSAH. The study design has been carefully balanced in order to optimise the detection of any treatment effects whilst minimising participant inconvenience.

The treatment periods are relatively short (6 weeks) but benefits of both MAD and CPAP in terms of subjective sleepiness and measures of cardiovascular risk have previously been demonstrated within this time frame[20, 21]. An acclimatisation period (2 weeks) is incorporated into each treatment to allow the participant time to get used to each device. The telephone call at the end of this period will allow the assessment of device tolerability and retention, and provide an opportunity for the trial team to encourage continued participation in the trial even if the current treatment is proving intolerable or ineffective. A wash-out period of one week will follow each active treatment period to ensure no carryover effects from the previous device. Existing evidence suggests that this is sufficient for physiological measurements (AHI) and symptoms to return to baseline [22-24].

We recognise that the study schedule places a high burden on participants with the number of visits required. The cross-over design will allow patients to trial a different device within a relatively short period of time if they find one device problematic. Participants will benefit from close surveillance of their condition throughout the trial through regular contact with the research team and will be supported through a telephone support line. All patient travel expenses will be reimbursed.

Adherence was a consideration in the statistical analysis of the study. The randomisation strategy ensures that patients who have completed at least two treatment periods can be included in the analysis. The data will be analysed on an intention to treat basis.

9. Monitoring and audit

The study will be monitored and audited by a representative from our Research & Development Department and/or local West Anglian Comprehensive Local Research Network (CLRN) who are independent of the trial.

A Trial Steering Committee (TSC) will be convened to monitor the progress of the trial, ensure all objectives are met, review all relevant information or amendments, and investigate any recommendations to the protocol. The TSC will consist of at least two external OSAH experts and a patient representative.

A Data Monitoring and Ethics Committee will meet twice a year (or as required) to ensure the safety, rights and well-being of participants are safe-guarding. An independent chair and clinician will attend the meetings.

10. Adverse and Serious Adverse Event Reporting

